9.5 Interim Monitoring and Analyses

The estimates of the common standard deviations used in the sample size calculation will be checked after the first 30 participants have been randomised and completed follow-up. This blinded internal pilot is not deemed to have any significant impact on the final analysis. If the standard deviation is smaller than that used in the sample size calculation, suggesting that fewer patients were required than initially proposed, then no action will be taken and the size of the study will remain as planned. If the standard deviation is larger than assumed suggesting the need for more patients then on the advice of the Data Monitoring Committee, the Trial Steering Committee will aim to increase recruitment and consider implications for funding and existing resources.

Missing data will be monitored and strategies developed to minimise its occurrence, however as much data as possible will be collected about the reasons for missing data and this will be used to inform any imputation approaches employed.

9.6 Analysis Plan

The study will be analysed and reported following the 'CONSORT' guidelines (Consolidated Standard of Reporting Trials)⁽³⁸⁻⁴¹⁾.

Data from all the study children will be analysed on completion of the study (T12W) on an intention to treat basis.

All analyses will be pre-specified in detail in the statistical analysis plan and agreed by both the Trial Steering Committee and the Data Monitoring Committee prior to the internal pilot.

Missing data will be handled by considering the robustness of the complete case analysis to sensitivity analyses using various imputation assumptions; however these will be informed by data collected on the reasons for missing data.

9.6.1 Sub-study Data Analysis

Statistical methodology for investigating genetic associations is a field that is developing at a rapid pace; however there is not as yet consensus as to the most effective methods. Traditional methodologies alone are not sufficient to deal with the complexities associated with the modelling of relationships between genetic profile and outcome, and the lack of success reported by reviewers of recent association studies is in part due to inadequate statistical analysis. The most up to date statistical

methods will be applied to the data in order to extract the maximum information possible.

Prior to the association analyses, a test for Hardy-Weinberg Equilibrium (HWE) will be undertaken at each SNP genotyped. Any marker found to deviate significantly from HWE (after accounting for multiple testing) will be excluded from the analyses. However, the reason for the deviation e.g. population substructure or genotyping error will be investigated. Population substructure will also be tested for by genotyping a minimum of 20 additional SNPs known to be independent of the SNPs of interest⁽⁴²⁾. SNPs found to have minor allele frequency of less than 1% will also be excluded from the analyses.

In order to capture putative SNPs not on the 370k chip, a data imputation method such as that described by Marchini et. al.⁽⁴⁵⁾ will be used to impute genotype data for the SNPs not included on the chip. These imputed genotypes will be tested for association in exactly the same way as the SNPs actually genotyped.

For the purpose of analysing the outcomes of interest, univariate analyses will first of all be undertaken to test for association with each SNP. The chi-squared or Fisher's exact test will be used for binary outcomes as appropriate, ANOVA will be used for continuous outcomes and the log-rank test will be used for time to event outcomes. Due to the huge number of SNPs being genotyped, multiple testing is obviously a key issue and so in addition to the p-values resulting from the univariate tests for association, a Bayes' Factor⁽⁴⁶⁾ will also be calculated to assess the strength of the evidence of association. A priori weights, calculated with reference to factors such as functional knowledge and linkage disequilibrium information will be applied to the Bayes' factor in order to reflect the relative weight of evidence attached to each SNP.

The univariate analyses will be followed by multiple regression analyses where regression models will be built for each gene separately. Logistic regression will be used for binary outcomes, linear regression will be used for continuous outcomes and proportional hazard models (with the assumption of proportional hazards being validated) will be used for time to event outcomes. Finally, regression models for each chromosome will be built, to include covariates representing SNPs within each gene found to be statistically significant in the per-gene analyses. If it is felt necessary due to the substantial number of SNPs contributing to each regression model, prior to building the models an assessment of the extent of linkage disequilibrium (LD) between the individual SNPs will be made and only one SNP from any group of SNPs found to be in strong LD will be included in the models in order to reduce the problems of collinearity and model overfitting. Backward selection will also be applied to the regression models to reduce these problems further. The models will initially include covariates to represent SNP main effects only, however once main effects are found to be statistically significant, SNP-SNP and SNP-environment interaction terms will be introduced into the models and tested for significance.

In all analyses, additive genetic effects will be assumed in the first instance. However, for the SNPs found to have a significant effect on outcome, dominant effects will then be added to the regression models to assess whether they have any additional effect.

If it is deemed appropriate, the above traditional regression methods will be supplemented with more recently developed statistical methods used specifically in genetic association studies.

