8.5 Substudies

8.5.1 Genetic Study

Whilst we know that melatonin secretion is highly heritable in humans (suggesting genetic reasons may be more important than environmental factors) no specific genetic cause had been identified. Mutations in ASMT, which encodes the last enzyme in the pathway that produces melatonin have now been described⁽³⁷⁾. Corresponding low levels of melatonin and sleep disorders are seen in the families where these mutations are found. The link is particularly strong in populations with learning difficulty and autism, where it has been speculated that additional mutations in neuroligins lead to an increased susceptibility to sleep disorders.

The ability to detect genetic variations that account for abnormal melatonin production has been described by the Human Genetics and Cognitive Functions laboratory at the Pasteur Institute, France, and some candidate genes have been identified. The first group of candidate genes are those encoding the enzyme synthesising melatonin (TPH2, AA-NAT, ASMT) and the receptors of the melatonin (MTNR1A, MTNR1B, GPR50). The second group are genes thought to play a role in the aetiology of both autistic spectrum disorders and learning difficulties, both of which markedly increase the risk of sleep disorders (NLGN, MAOA, MAOB, COMT, SLC6A4, GABAR).

We are working with the Pasteur Institute on a genome-wide association (GWA) study, the aim being to identify genetic variants, initially within the aforementioned candidate genes and then also across the remaining genomic regions, associated with abnormal melatonin production and subsequently with sleep disorder.

Single Nucleotide Polymorphisms (SNPs) across the genome will be genotyped using the patient's DNA from a simple saliva sample. Genotyping will be undertaken using Illumina's HumanCNV370-Duochip ('370k chip') by the Human Genetics and

Cognitive Functions team, who already have an impressive track record in this field and all the facilities for rapid, blinded, genotyping. The 370k chip captures 81% and 68% of HapMap genetic variants at $r^2 > 0.8$, in Caucasian and Asian populations respectively. It therefore provides high genomic coverage of the known human genome SNPs.

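### Three fixed rules of the genetic sub-study do not fit its genome-wide chip design: 20 extra SNPs for substructure, one Hardy-Weinberg filter for every marker, and ANOVA as the first test

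*Protocol*

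**What the plan says.** Section 8.5.1 sets out a genome-wide association study, candidate genes first and then the rest of the genome, on a 370k chip: "Single Nucleotide Polymorphisms (SNPs) across the genome will be genotyped".

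Section 9.6.1 then fixes these rules:

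- **Substructure.** "Population substructure will also be tested for by genotyping a minimum of 20 additional SNPs known to be independent of the SNPs of interest".
- **Hardy-Weinberg filter.** Before any association analysis, "a test for Hardy-Weinberg Equilibrium (HWE) will be undertaken at each SNP genotyped". The consequence of failing that check is laid down at once: "Any marker found to deviate significantly from HWE (after accounting for multiple testing) will be excluded from the analyses". The next sentence adds that causes such as substructure or genotyping error will be looked into. It gives no route by which an excluded marker returns.
- **First-stage test.** Each SNP is first tested on its own, by chi-squared or Fisher's exact test for binary outcomes and the log-rank test for time-to-event outcomes; "ANOVA will be used for continuous outcomes". Imputed genotypes are to be tested identically to typed ones.
- **Genetic model.** "In all analyses, additive genetic effects will be assumed in the first instance". Dominance is added later, in the regression models, for SNPs already found significant.

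The regression models start with SNP main effects and may gain SNP-SNP and SNP-environment interactions and dominance. No ancestry covariate is named.

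**The concern.** These are written rules, not details left open. A SAP that follows them takes over their weaknesses, and one that departs from them disagrees with the protocol. They govern secondary outcome 13 (genetic variants and abnormal melatonin production) and the sub-study's other association questions.

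- A set of 20 SNPs outside the SNPs of interest suits a candidate-gene study. In a scan of the whole genome that outside set is nearly empty, and a panel this small can miss structure large enough to distort the associations. A positive result is also tied to no adjustment.
- A boy has one copy of an X-linked SNP and cannot be heterozygous. One HWE test over both sexes can therefore reject sound X-linked markers, and the written consequence is exclusion.
- ANOVA over three unordered genotype groups spends a second degree of freedom on dominance before the additive effect has been tested, which reverses the order the section sets.

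**Working it through.** The sub-study states no sample size, power or significance level, so there is no figure of its own to reproduce.

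**Inputs.** From the protocol: the 370k chip, at least 20 extra SNPs, HWE at each SNP with multiplicity adjustment, ANOVA, and additivity first. Assumed: 114 genotyped children (the trial's randomisation target; section 8.5.1 genotypes all children initially recruited and gives no number), with 86 and 160 as a range; boys 50% to 70%; HWE threshold 0.05/370,000 = 1.35e-7, for which the 1-df critical chi-square is 27.8.

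**1. Power of the substructure test.** Sum L independent 1-df chi-squares and reject above c, the upper 5% point of chi-square on L df. If structure inflates each statistic by a factor λ, power = P(χ²_L > c/λ). The relative standard error of the estimated inflation is √(2/L); for L = 20 this is √0.1 = 0.32.

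| λ | 20 SNPs | 10,000 independent chip SNPs (assumed count) |
|---|---|---|
| 1.05 | 0.07 | 0.96 |
| 1.1 | 0.10 | 1.00 |
| 1.2 | 0.16 | 1.00 |
| 1.5 | 0.40 | 1.00 |
| 2.0 | 0.74 | 1.00 |

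**2. HWE on an X-linked SNP, sexes pooled, boys scored as homozygous.** Let m be the share of boys and p, q the allele frequencies. Only girls can be heterozygous, so the observed heterozygote share is (1 − m)·2pq against 2pq expected. Hence F = 1 − (1 − m) = m, and the expected chi-square is about N·F² = N·m².

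- m = 0.5: 114 × 0.25 = 28.5
- m = 0.6: 114 × 0.36 = 41.0
- m = 0.7: 114 × 0.49 = 55.9

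All exceed 27.8, but the first only just, so simulation is needed for the share excluded (20,000 SNPs per setting, minor allele frequency uniform from 0.05 to 0.50):

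| N | 50% boys | 60% boys | 70% boys |
|---|---|---|---|
| 86 | 23% | 65% | 93% |
| 114 | 50% | 89% | 98% |
| 160 | 86% | 98% | 99.7% |

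A looser threshold excludes more: at 1e-6 and N = 114, 66% with half boys and 94% with 60% boys. Tested in girls only at the 1.35e-7 threshold, under 0.1% are excluded in every setting of the table.

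**3. First-stage test for a truly additive SNP.** Non-central F with non-centrality N·R²/(1 − R²). For R² = 5% and N = 114 this is 114 × 0.05/0.95 = 6.0. Compare 1 and 112 df (additive) with 2 and 111 df (three genotypes).

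| R² | alpha | 1 df | 2 df |
|---|---|---|---|
| 5% | 0.05 | 0.68 | 0.57 |
| 10% | 0.05 | 0.94 | 0.89 |
| 20% | 1.35e-7 | 0.40 | 0.29 |

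Two practical points lead the same way. At a minor allele frequency of 5%, the chance that none of 114 children is a minor homozygote is (1 − 0.05²)^114 = 0.75, so the third ANOVA group is often empty. Imputed genotypes kept as non-integer dosages do not form ANOVA groups at all.

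**The case against.** Each point has a stronger reading that the protocol does not support.

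- *That 20 SNPs take the place of the chip's ancestry information, so associations will be confounded.* The sentence is worded as an additional step with a lower bound, and nothing forbids using chip markers. The section also promises up-to-date methods and allows newer ones as a supplement. The protocol gives no ancestry mix, so no inflated error rate can be claimed. What stands is that the only substructure test written down is weak, is defined in a way that does not suit a whole-genome scan, and leads to no term in the models.
- *That the X chromosome will be silently lost.* The protocol does not say that the sexes are pooled or how boys are coded, and girls-only testing is routine quality control that a SAP or the laboratory could supply. Causes of deviation are to be investigated, so a run of failures on one chromosome should be noticed. What stands is that the literal rule covers every marker and that investigation does not reverse exclusion.
- *That ANOVA contradicts the additive model.* A 1-df linear trend can be run within ANOVA, and the additive sentence can be read as setting the coding for it. What stands is that ordinary ANOVA is the 2-df form, no coding is given, and the two statements do not fit together as they are.

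It is also fair to say that the sub-study is exploratory and comes last of 13 secondary outcomes.

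**Conclusion.** The concern holds in this limited form: section 9.6.1 fixes three rules that suit the genome-wide design poorly and have better, inexpensive alternatives.

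The substructure rule is the firmest point. Power of 0.10 to 0.16 at inflation of 1.1 to 1.2 depends only on the 20 SNPs being independent and on a 5% test. The chip comparison also assumes 10,000 independent SNPs. The HWE point is conditional on pooled sexes and boys scored as homozygous. The loss of 50% to 89% further assumes 114 children, 50% to 60% boys and the 0.05/370,000 threshold, and it falls to 23% with 86 children and half boys. The ANOVA point is an inconsistency costing about 0.11 in power (0.68 − 0.57) in the 5% variance case.

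The rules should be changed before the genetic data are analysed. The primary outcome, the treatment comparison and the safety analysis are not affected.

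**What to change.** Amend section 9.6.1 as follows.

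1. Replace the 20-SNP step with principal components computed from LD-pruned autosomal chip SNPs, and include a small, pre-set number of leading components as covariates in the association models. This costs a few degrees of freedom and saves the extra genotyping.
2. Test HWE for autosomal SNPs in all children and for X-linked SNPs in girls only. The X-linked test then rests on fewer children (57 of 114 if half are girls), so it is less sensitive to genotyping error.
3. Make the first-stage test a 1-df additive test: linear or logistic regression on allele count, or on dosage for imputed SNPs, with the genotypic test as follow-up. For any time-to-event outcome, use the proportional hazards model the section already names. Regression at this stage also lets the ancestry components enter, which ANOVA, chi-squared and log-rank tests in their plain form do not.

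The change is a few sentences and needs no new data.

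### Testing imputed SNPs exactly as measured ones implies best-guess genotypes in the univariate step, which loses some information; dosage regression is a cheap improvement

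*Protocol*

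**What the plan says.** All of this is in the protocol.

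- **Imputation and testing (section 9.6.1).** Genotypes are imputed for SNPs absent from the 370k chip. The instruction for testing them is: "These imputed genotypes will be tested for association in exactly the same way as the SNPs actually genotyped".
- **Univariate tests (section 9.6.1).** "The chi-squared or Fisher's exact test will be used for binary outcomes as appropriate, ANOVA will be used for continuous outcomes". Survival-type outcomes are compared by log-rank.
- **Later modelling (section 9.6.1).** Logistic, linear and proportional hazards regressions follow, per gene and then per chromosome. Additive effects are assumed first in all analyses.
- **Marker checks (section 9.6.1).** Before any association testing, "a test for Hardy-Weinberg Equilibrium (HWE) will be undertaken at each SNP genotyped". Rare variants are dealt with separately: "SNPs found to have minor allele frequency of less than 1% will also be excluded from the analyses". A Bayes' factor with prior weights accompanies the p-values.
- **Stated aim (section 9.6.1).** The section promises current techniques: "methods will be applied to the data in order to extract the maximum information possible".
- **Chip coverage (section 8.5.1).** "The 370k chip captures 81% and 68% of HapMap genetic variants". The threshold is r² > 0.8; the first figure is for Caucasian populations and the second for Asian ones.

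The section does not mention dosages, genotype probabilities or multiple draws.

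**The concern.** For each child and SNP, imputation yields a probability for each of the three genotypes. A contingency-table test, a one-way ANOVA or a log-rank comparison by genotype cannot use those probabilities. Each child must be placed in one group. Doing to imputed SNPs exactly what is done to measured ones therefore means calling the most likely genotype and treating it as observed.

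Two things are at stake. A call correlates less well with the true genotype than the expected allele count does, so power falls beyond what imperfect imputation already costs. The per-allele effect estimated from calls is also pulled towards zero. Both sit awkwardly with the section's aim of extracting all the information available, and with its additive model, which dosage fits directly.

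The protocol states this as a rule. It is not a detail left open for the SAP.

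**Working it through.** The sub-study states no sample size, power or significance level, so there is no figure of its own to reproduce.

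**Inputs**

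- From the protocol: the univariate tests, the additive model, and 114 randomised children (57 per group, section 9.4). The 114 is used only as an illustrative n. The sub-study genotypes all children initially recruited, so its n may differ.
- Assumed: imputation r² from 0.3 to 0.95; minor allele frequency (MAF, written q) of 0.05, 0.10 and 0.30; and, for power, a SNP explaining 6.5% of outcome variance.

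**Model.** Each of a child's two haplotypes has an allele probability p drawn from Beta(aq, a(1−q)) with a = 1/r² − 1. The true allele is Bernoulli(p), and the true genotype is the sum of the two alleles. The dosage is P(1 copy) + 2·P(2 copies). The call is the genotype with the highest probability.

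**Step 1. Information and attenuation.** With 600,000 simulated individuals per cell, the squared correlation of the call with the true genotype, and the regression slope of true genotype on call, were:

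| Imputation r² (dosage) | Call, MAF 0.05 | Call, MAF 0.10 | Call, MAF 0.30 | Slope on call |
|---|---|---|---|---|
| 0.50 | 0.38 | 0.39 | 0.41 | 0.69–0.72 |
| 0.80 | 0.74 | 0.74 | 0.74 | 0.87 |
| 0.90 | 0.86 | 0.87 | 0.87 | 0.93 |
| 0.95 | 0.93 | 0.93 | 0.93 | 0.97 |

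Repeat runs differ by about 0.01, giving 0.37 to 0.41 overall in the first row. The slope on dosage is 1.00 throughout. Calling therefore understates the per-allele effect by about 30% at r² 0.5 (1 − 0.70), 13% at 0.8 (1 − 0.87) and 7% at 0.9 (1 − 0.93).

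**Step 2. Effective sample size,** n × squared correlation, at n = 114 and MAF 0.30. At r² 0.5, dosage gives 114 × 0.50 = 57 and the call gives 114 × 0.41 = 47. At r² 0.9 the figures are 102 and 99.

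**Step 3. Power and error,** 6,000 replicates, n = 114, MAF 0.30, alpha 0.05 for illustration.

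| Imputation r² | Dosage regression | Regression on call | ANOVA on call |
|---|---|---|---|
| 0.5 | 0.49 | 0.42 | 0.32 |
| 0.7 | 0.64 | 0.59 | 0.48 |
| 0.9 | 0.75 | 0.73 | 0.62 |

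Only the gap between the first two columns is due to calling. The further drop to ANOVA comes from spending 2 degrees of freedom where the additive test spends 1. Over r² 0.3 to 0.7 and MAF 0.10 and 0.30, calling alone costs about 5 to 11 percentage points; at 0.9 or above it costs 1 to 2. Under the null, rejection rates were 0.045 to 0.057 for every method.

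**Step 4. After multiplicity.** With the same n and effect and an assumed 1,000 tests (alpha 0.05/1,000 = 0.00005), power is 9% with perfect genotypes. At r² 0.5 it is 1.5% with dosage and 0.9% with calls (squared correlation 0.41).

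**The case against.** The case for leaving the text alone has several parts.

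- **The regressions are not tied to calls.** An additive term takes an expected allele count as readily as 0, 1 or 2. This stands. A reader might infer that best-guess calls are forced on the whole genetic analysis, but the documents support that only for the univariate step.
- **The chip figures are not imputation accuracy.** A reader might take the uncaptured 19% (100 − 81) or 32% (100 − 68) to mean that many imputed SNPs will be poor. Section 8.5.1 describes chip coverage. It does not say how well the remaining variants would be imputed, so that inference is unsupported.
- **Large losses can be shown only by assuming poor imputation.** At r² 0.3 the call keeps 0.15 to 0.22, but nothing in the protocol says SNPs of that quality would be common, and a usual quality cut-off would sit near that value.
- **Imputed SNPs need not be given equal standing.** The weighted Bayes' factor is meant to reflect differing strength of evidence by SNP. It is not an imputation-quality filter, but it counts against saying that all SNPs are treated alike.
- **A quality threshold is SAP material.** This stands. Its absence from the protocol is not a fault.
- **Little would be gained in detections.** Step 4 bears this out. Absolute power is very low either way.

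The permission to add newer genetic methods does not answer the point. It is discretionary, it supplements the regressions, and it leaves the testing instruction in place.

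**Conclusion.** The point holds in a limited form and is minor. As worded, the univariate step needs best-guess genotypes for imputed SNPs, and the protocol does not say that dosages may be used later. The cost is attenuated effects and some lost power: material at imputation r² around 0.5, modest at 0.8, and small at 0.9 or above. These sizes rest on assumed accuracy, allele frequencies, effect size and n, and on a simple haplotype model. The protocol gives no distribution of accuracy, so the average loss cannot be stated.

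A reader might infer that calling produces false associations or threatens the trial's result. Neither follows. Null rejection rates stayed near 5%, and the primary outcome and main comparison are untouched.

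**What to change.** Replace the sentence in section 9.6.1 with:

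> Imputed SNPs will be analysed, at both the univariate and multivariable stage, by regression (linear, logistic or proportional hazards) on expected allele dosage under the additive model, and results for imputed SNPs will be flagged with their imputation quality.

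Any quality cut-off can be set in the SAP.

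The cost is one sentence and no new data. There are two drawbacks. Imputed and measured SNPs would no longer share the same univariate test, and poorly imputed SNPs may go untested if a cut-off is applied.

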In order to make sense of genotype phenotype correlations, large populations, defined by as much objective data as possible, are required. The MENDS study is gathering objective actigraphic and salivary melatonin data on children who enter the study and the population we are studying is precisely the group where genetic mutations specific to melatonin production might be expected. The MENDS sub-study aims to address the following:

- (i) what is the nature of any association between sleep problems and melatonin levels?
- (ii) can we identify genetic markers associated with the severity of the sleep problem and/or melatonin level?
- (iii) can we identify genetic markers that are associated with an individual's ability to synthesise melatonin?
- (iv) can we identify genetic markers that are associated with an individual's response to melatonin treatment in sleep disorders?

This sub-study will therefore involve genotyping of all children initially recruited to the project with sleep disorders and developmental delay. As preliminary data suggests that autism may be particularly strongly associated with these genetic mutations, we will precisely define this subgroup using the Social Communication Questionnaire. If the questionnaire suggests the presence of autism in a child with no previous diagnosis a letter will be sent to the referring clinician highlighting this (Appendix J).

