8.6.3.2 DNA analysis

After fully blinded genotyping has taken place, the results of the genotyping will be correlated with the salivary melatonin concentration, actigraphy results and clinical phenotype of the individuals. For the clinical phenotype outcomes, two approaches will be taken. Firstly, association with the primary outcome of the trial will be undertaken. Secondly, mutually exclusive subgroups will be defined (without reference to the genotyping results) with regard to a combination of the CSHQ, actigraphy and dim-light melatonin onset (DLMO) salivary sample results. The disorders most relevant to endogenous melatonin production will be Circadian rhythm sleep disorders (CRSD) either advanced, delayed or free-running.

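### The genetic sub-study asks which markers predict response to melatonin, but tests interactions only after a significant SNP main effect and never names treatment arm, so it can miss such markers

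*Protocol*

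**What the plan says.** Protocol 8.5.1 lists four aims for the genetic sub-study. The fourth is: "can we identify genetic markers that are associated with an individual's response to melatonin treatment in sleep disorders".

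Protocol 9.6.1 then sets out one sequence of analyses for the sub-study:

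- First, "univariate analyses will first of all be undertaken to test for association with each SNP".
- Next come regressions for each gene, then for each chromosome. "The models will initially include covariates to represent SNP main effects only".
- Interactions come last: "once main effects are found to be statistically significant, SNP-SNP and SNP-environment interaction terms will be introduced into the models and tested for significance".
- At the end there is a discretionary clause: "If it is deemed appropriate, the above traditional regression methods will be supplemented with more recently developed statistical methods".

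Protocol 8.6.3.2 adds, for the clinical phenotype: "Firstly, association with the primary outcome of the trial will be undertaken". Neither section names treatment arm, either as a covariate or as one of the environmental factors.

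**The concern.** Response to a drug in a randomised trial is a contrast between arms: how much the treatment effect changes with genotype. The parameter that answers question (iv) is therefore the SNP-by-treatment interaction.

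The written sequence puts a different parameter first. A SNP main effect on a post-randomisation outcome, pooled over arms, averages the SNP's effect under melatonin and under placebo. It can be large for a marker that predicts sleep regardless of treatment, and small or zero for a marker that changes the effect of melatonin. Used as a gate, it can let purely prognostic markers through and stop markers of the kind question (iv) is looking for.

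At stake is the answer to one exploratory question. The trial's primary and secondary treatment comparisons do not depend on it.

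**Working it through.** **Inputs from the protocol.** Equal allocation (7.1). SD 1.7 h, difference 1 h, 47 evaluable per group, two-sided 0.05, 80% power (9.4). A chip described as 370k (8.5.1).

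**Assumptions.** The protocol gives no allele frequency, no per-allele effect, no sub-study sample size and no significance threshold for the SNP tests. I assume an additive SNP, allele frequency p = 0.3, effects of 0.5 to 1 h per allele, N = 94 (2 × 47) and, where a genome-wide threshold is needed, Bonferroni over 370,000 SNPs. N = 94 is optimistic, because DNA has its own consent (11.3.2.3).

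**The plan's own figure.** For 1 h and SD 1.7, the t-test has 79.7% power at 46 per group and 80.6% at 47. The stated 47 reproduces.

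**The two tests.** Let b_M and b_P be the per-allele effects under melatonin and placebo, and sd_g = √(2p(1−p)) = √0.42 = 0.648.

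- Pooled main effect: (b_M + b_P)/2, standard error SD/(√N · sd_g).
- Interaction: b_M − b_P, standard error 2·SD/(√N · sd_g).

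In a balanced design the two estimates are independent, so the chance of passing the gate and then detecting the interaction is the product of the two powers.

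*Active under melatonin only, b_M = 1, b_P = 0.* Main-effect z: 0.5 × 9.695 × 0.648/1.7 = 1.85. Interaction z: 1 × 9.695 × 0.648/3.4 = 1.85. They are equal.

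*Equal and opposite effects.* The main-effect z is exactly 0, so the gate is passed at its alpha and no more.

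With 0.05 at both stages and N = 94 (simulation: 4,000 runs):

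| Effect per allele (melatonin, placebo) | Gate passed | Interaction, direct | Gate and interaction | Simulated: direct, gated |
|---|---|---|---|---|
| +1 h, 0 | 46% | 46% | 21% | 43%, 18% |
| +0.75 h, −0.25 h | 15% | 46% | 6.9% | 43%, 6.2% |
| +0.5 h, −0.5 h | 5% | 46% | 2.3% | 43%, 2.1% |
| +1 h, −1 h | 5% | 96% | 4.8% | 94%, 5.5% |

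With all 114 randomised children, direct against gated detection is 53% against 28% (row 1), 53% against 2.7% (row 3) and 98% against 4.9% (row 4).

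**Does the loss in row 1 survive a multiplicity correction?** With the same alpha at both stages, gating squares the power: 0.80² = 64%, 0.50² = 25%. A genome-wide search need not use the same alpha, because a gate leaves fewer interactions to correct for. For a melatonin-only marker (equal z at both stages):

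- Ungated, alpha 0.05/370,000, critical value 5.27. Power of 80% needs z = 5.27 + 0.84 = 6.11; power of 50% needs z = 5.27.
- Gate at 0.05, which about 0.05 × 370,000 = 18,500 SNPs pass by chance; survivors tested at 0.05/18,500, critical value 4.69. Power is Φ(6.11 − 4.69) = 92% and Φ(5.27 − 4.69) = 72%, with the gate passed almost surely.
- Gate at 0.05/370,000, survivors tested at 0.05: 80% and 50%, unchanged.

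So for this pattern the gate can cost power, cost nothing or gain power, depending on a rule the protocol does not give.

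**What is attainable at this size.** At 0.05/370,000 and N = 94, the direct interaction test for row 1 has about 0.03% power. With the 0.05 gate and 0.05/18,500 for survivors it has 46% × Φ(1.85 − 4.69) ≈ 0.1%. Neither is useful genome-wide.

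**The case against.** The strongest reply is that gating on a main effect is a legitimate screen. The two statistics are independent, so screening does not distort the second test, and it lightens the correction. The working bears this out for a melatonin-only marker. A reader might infer from the 64% and 25% figures that the gate always loses power; those figures hold only when both stages use the same alpha. What remains is the opposite-direction pattern, which no multiplicity rule rescues, and the protocol gives no reason to expect that pattern to be common.

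Second, 9.6.1 is a general pipeline, and 9.6 leaves detail to an analysis plan that was not available here. The references to responders and non-responders (8.6.3.1, 11.1) might point to an analysis among treated children, where the pooled-arm arithmetic would not apply. That is possible but not stated, and a melatonin-only analysis would still not tell prognosis from drug response. The order of testing is not left open: the protocol fixes it.

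Third, treatment could count as an environmental factor, and supplementary methods are allowed. The first reading leaves the interaction behind the gate. The second is discretionary and commits to no ungated test.

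Fourth, the consequence is small. The genetic outcome listed among the secondary outcomes (4.2, 9.3.2) concerns abnormal melatonin production, which this argument does not touch. That stands.

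**Conclusion.** The point holds as a mismatch between question (iv) and the fixed sequence in 9.6.1. As written, the main-effect stage mixes prognostic with drug-response markers, and nothing in the protocol commits to an ungated test. The firm loss is for markers with opposite effects in the two arms: exactly opposite effects pass the gate at its alpha, so detection cannot exceed about 5% at a 0.05 gate, against 46% to 96% for a direct test at 0.05 in the examples. For melatonin-only markers the direction of the effect on power is undetermined. These sizes rest on the assumed allele frequency, per-allele effects and N = 94.

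Three stronger readings are not supported:

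- That the sub-study cannot identify response markers at all. A melatonin-only marker keeps half its effect at the gate, and if treatment counts as environment its interaction could then be tested. The right strength is that the plan can miss them.
- That imputation error is ignored because "These imputed genotypes will be tested for association in exactly the same way as the SNPs actually genotyped". This may mean only that the same tests are used; the imputation method is cited, and whether it carries genotype uncertainty forward cannot be judged from the protocol.
- That the check for population structure is inadequate because "Population substructure will also be tested for by genotyping a minimum of 20 additional SNPs known to be independent of the SNPs of interest". The figure is a minimum, Hardy-Weinberg deviations are also investigated, and a preference for another method is not an error in the plan.

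The matter is minor: worth correcting, with no bearing on the trial's main conclusions.

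**What to change.** In 9.6.1 (or the analysis plan, with 9.6.1 amended to agree):

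1. For question (iv), restrict to randomised children and fit the outcome on baseline sleep, treatment arm, additive SNP and SNP × treatment.
2. Test the SNP × treatment term whether or not the SNP main effect is significant.
3. Take the candidate genes named in 8.5.1 first, then the rest of the genome.
4. State a multiplicity rule for these interaction tests. The Bayes' factor in 9.6.1 is tied to the univariate association tests and does not cover them.
5. Label the analysis exploratory.
6. Include treatment arm in every model of a post-randomisation outcome.

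The cost is wording and analysis time; no new data or visits are needed. The downside is more tests, and genome-wide power for interactions that stays very low at this sample size, which is the reason for putting candidate genes first and for the exploratory label.
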